#### 8.6.3.3 EXPECTEDNESS

The Investigator will be responsible for determining whether an AE is expected or unexpected. XTMAB-16 has not previously been administered in humans. [REDACTED]

[REDACTED]

[REDACTED]

[REDACTED]

#### 8.6.4 TIME PERIOD AND FREQUENCY FOR EVENT ASSESSMENT AND FOLLOW-UP

The occurrence of an AE or SAE may come to the attention of CRU personnel during study visits and interviews of a participant presenting for medical care, or upon review by a study monitor.

All AEs including local and systemic reactions not meeting the criteria for SAEs will be captured on the appropriate eCRF. Information to be collected includes event description, time of onset, clinician's assessment of severity, relationship to study product (assessed only by those with the training and authority to make a diagnosis), and time of resolution/stabilization of the event. All AEs occurring while on study must be documented appropriately regardless of relationship. All AEs will be followed to adequate resolution.

Any medical condition that is present at the time that the participant is screened will be considered as Baseline and not reported as an AE. However, if the participant's condition deteriorates at any time during the study, it will be recorded as an AE.

Changes in the severity of an AE will be documented to allow an assessment of the duration of the event at each level of severity to be performed. AEs characterized as intermittent require documentation of onset and duration of each episode.

The Investigator or designee will record all reportable events with start dates occurring any time after informed consent is obtained until 7 (for nonserious AEs) or 30 days (for SAEs) after the last day of study participation. At each study visit, the Investigator will inquire about the occurrence of AE/SAEs since the last visit. Events will be followed for outcome information until resolution or stabilization.

#### 8.6.5 SERIOUS ADVERSE EVENT REPORTING

The PI or designee is responsible for providing notification to the Sponsor of any SAE, whether deemed study drug-related or not, that a participant experiences during the study within 24 hours of becoming aware of the event.

As a minimum requirement, the initial notification should provide the following information:

- Study number
- Participant number
- Sex
- Date of birth
- Name of PI and full CRU address
- Details of SAE
- Criterion for classification as 'serious'
- The study drug name, or code if unblinded, and treatment start date
- Date of SAE onset
- Causality assessment (if sufficient information is available to make this classification)

All SAEs will be followed until satisfactory resolution, until the Investigator deems the event to be chronic, or the participant is stable. Other supporting documentation of the event may be requested by Parexel Safety Services/Sponsor and should be provided as soon as possible.

The SAE form will be sent to:

**Parexel Safety Services**  
Email: [REDACTED]  
FAX: [REDACTED]

The Sponsor will be responsible for notifying regulatory authorities (eg, FDA, EMA, as applicable) of any unexpected fatal or life-threatening suspected adverse reaction, suspected unexpected serious adverse reaction (SUSAR), or other applicable SAE as soon as possible, but in no case later than 7 calendar days after the Sponsor's initial receipt of the information. In addition, the Sponsor must notify regulatory authorities and all participating Investigators in an IND safety report of potential serious risks, from clinical trials or any other source, as soon as possible, but in no case later than 15 calendar days after the Sponsor determines that the information qualifies for reporting.

The Sponsor will notify the Investigator of relevant information about SUSARs that could adversely affect the safety of participants in a timely fashion. Follow-up information may be submitted if necessary. The Sponsor will also provide annual safety reports for submission to the regulatory authority and the IRB/IEC responsible for the clinical study. These updates will include information on SUSARs and other relevant safety findings.

#### 8.6.6 EVENTS OF SPECIAL INTEREST

Based on clinical data from the TNF $\alpha$  inhibitor package inserts and nonclinical data to date for XTMAB-16, the adverse event of special interest (AESI) for this study is:

- Anaphylactic shock

AESIs will be reported using the appropriate eCRF. In addition, AESIs that are also SAEs will be reported using the SAE form and sent to Parexel Safety Services (see Section 8.6.5).

#### 8.6.7 REPORTING OF PREGNANCY

- The Investigator will collect pregnancy information on any female participant or female partner of a male participant who becomes pregnant while the participant is in this study.
- If a pregnancy is reported, the Investigator should inform Parexel Safety Services within 24 hours of learning of the pregnancy using the SAE Form.
- If a pregnancy occurs, the participant will be followed to determine the outcome of the pregnancy, but no longer than 6-8 weeks after the estimated delivery date. Any termination of pregnancy will be reported, regardless of fetal status (presence or absence of anomalies) or indication for the procedure.
- Pregnancy is not considered an SAE but should be reported in the eCRF and on the Pregnancy Form in accordance with SAE reporting timelines as per Section 8.6.5. Abnormal pregnancy outcomes (eg, spontaneous abortion, fetal death, stillbirth, congenital anomalies, and ectopic pregnancy) are considered SAEs.
- Any post-study pregnancy-related SAE considered reasonably related to the study treatment by the Investigator will be reported to the Sponsor as per Section 8.6.5. While

the Investigator is not obligated to actively seek this information in former study participants, he or she may learn of an SAE through spontaneous reporting.

## 8.7 UNANTICIPATED PROBLEMS

### 8.7.1 DEFINITION OF UNANTICIPATED PROBLEMS

The Office for Human Research Protections (OHRP) considers unanticipated problems (UPs) involving risks to participants or others to include, in general, any incident, experience, or outcome that meets all of the following criteria:

- Unexpected in terms of nature, severity, or frequency given (a) the research procedures that are described in the protocol-related documents, such as the IRB-approved research protocol and informed consent form (ICF); and (b) the characteristics of the participant population being studied;
- Related or possibly related to participation in the research (“possibly related” means there is a reasonable possibility that the incident, experience, or outcome may have been caused by the procedures involved in the research); and
- Suggests that the research places participants or others at a greater risk of harm (including physical, psychological, economic, or social harm) than was previously known or recognized.

Investigators should refer to the Remicade (infliximab) package insert for known risks and AEs with the use of this class of drug (TNF $\alpha$  blockers).

### 8.7.2 UNANTICIPATED PROBLEM REPORTING

The Investigator will report UPs to the IRB and to Parexel Safety Services. The UP report will include the following information:

- Protocol identifying information: protocol title and number, PI’s name, and the IRB project number.
- A detailed description of the event, incident, experience, or outcome.
- An explanation of the basis for determining that the event, incident, experience, or outcome represents an UP.
- A description of any changes to the protocol or other corrective actions that have been taken or are proposed in response to the UP.

To satisfy the requirement for prompt reporting, UPs will be reported using the following timeline:

- UPs that are SAEs will be reported to the IRB and to the Parexel Safety Services within 24 hours of the Investigator becoming aware of the event.

- Any other UP will be reported to the IRB and to the Parexel Safety Services within 7 days of the Investigator becoming aware of the problem.

All UPs should be reported to appropriate institutional officials (as required by an institution's written reporting procedures), the supporting agency head (or designee), and the OHRP within 7 days of the IRB's receipt of the report of the problem from the Investigator.

## 9 STATISTICAL CONSIDERATIONS

### 9.1 STATISTICAL HYPOTHESES

Hypothesis testing will not be conducted for this study.

### 9.2 SAMPLE SIZE DETERMINATION

The selection of 24 participants (12 per cohort) was based on feasibility and precision around the estimates for target variables associated with the primary and secondary endpoints. No sample size calculation was performed.

### 9.3 POPULATIONS FOR ANALYSES

- **Enrolled Set (ES):** The ES will consist of all participants who have given informed consent.
- **Full Analysis Set (FAS):** The FAS will consist of all participants randomized into the study. Participants in this analysis set will be used for analyzing demographics and other baseline characteristics.
- **Safety Set:** The safety analysis set will consist of all participants who are randomized to treatment and have received 1 dose of study drug. Participants in this analysis set will be used for demographics, baseline characteristics, and safety summaries.
- **Pharmacokinetic Per-Protocol Set (PK-PPS):** The PK-PPS set will consist of all participants in the Safety Set who provide at least 1 quantifiable serum XTMAB-16 PK sample postdose without important protocol deviations that would affect the concentration.
- **Biomarker Set:** The PD set will consist of all participants in the PK-PPS who have at least 1 postdose biomarker measurement.

If any participants are found to be noncompliant in dosing schedule or with incomplete data, a decision will be made on a case-by-case basis as to their inclusion in the PK and biomarker analysis sets but nevertheless will be presented in the participant listings.

### 9.4 STATISTICAL ANALYSES

Statistical analysis and generation of tables, figures, study participant data listings, and statistical output will be performed using SAS® Version 9.4 or higher.

All original and derived parameters will be listed and described using summary statistics. For continuous parameters, number of participants with available measurements, mean, standard deviation (SD), median, minimum, and maximum and for categorical parameters, number of participants and percentages (to 1 decimal place) in each category will be presented.

All descriptive statistics will be presented by treatment where applicable (eg, biomarkers), including columns for all treated participants and all participants on demographics, baseline characteristics, and AE displays, and using the available data for the study population as observed. Summaries of concentration data will be based on geometric mean and geometric SD instead of arithmetic versions. All tabulations will be sorted by treatment, parameter, and Day (including time relative to dosing if applicable, unless otherwise stated). Only scheduled visits and times relative to dosing will be included in the tabulation.

Categorical data will be summarized by Day/Week/Time and treatment.

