#### 8.2.5 CLINICAL LABORATORY EVALUATIONS

Clinical laboratory assessments will be collected under appropriate conditions defined by the clinical unit's standard of practice.

- The research laboratory unit will be used to perform all clinical laboratory tests including serum pregnancy test, which will be assessed by the CRU staff. The Investigator should take immediate action for any safety concerns based on laboratory results.
- The Investigator must review the laboratory report, document this review, and record any clinically relevant changes occurring during the study in the eCRF. The laboratory reports must be filed with the source documents. Clinically significant abnormal laboratory findings are those that are not associated with an underlying disease, unless judged by the Investigator to be more severe than expected for the participant's condition.

- All laboratory tests with values considered clinically significantly abnormal during participation in the study, including the participant's last EOS visit, should be repeated until the values return to normal or Baseline or are no longer considered clinically significant or follow-up is no longer needed per the judgment of the Investigator or Medical Monitor.
  - If such values do not return to normal/Baseline within a period of time judged reasonable by the Investigator, the etiology should be identified, and the Sponsor notified.
- All protocol-required laboratory assessments, as defined in [Appendix 1](#), must be conducted in accordance with the Laboratory Manual and the SoA (Section [1.3](#)).

Blood volumes for laboratory samples will be included in the Laboratory Manual.

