4.2 General Presentation Considerations

This section is applicable to all non-PK assessments.

TLF outputs will be generated for XTMAB-16 and pooled placebo by the planned treatment duration.

The participants, who received “Placebo” in each cohort, will be pooled into a single placebo group (Pooled Placebo) in each respective part for all summaries and presentation related to safety for this study. The PK outputs will be generated for each XTMAB-16 dose.

‘Baseline’ is defined as the last observed value of the parameter of interest prior to dosing (this includes unscheduled visits) for each XTMAB-16 dose and pooled placebo group. ‘End of Study’ for a participant is defined as the last available post-treatment assessment. ‘Study Day’ will be calculated relative to the date of randomization i.e. Study Day = Assessment Date -Randomization Date + 1.

In case of any unscheduled repeated assessments occurred during the period, the following rule will be applied, unless specified otherwise:

If unscheduled repeated measurement of a specific parameter occurs prior to the first XTMAB-16 administration (Day 1), then the last obtained value prior to dosing will be considered in the descriptive statistics and in the calculation of change from baseline.

If unscheduled repeated measurement of a specific parameter occurs after Day 1 or XTMAB-16 or Placebo administration, then the first (non-missing) value after dosing will be used in descriptive statistics and in the calculation of change from baseline.

All data will be listed according to the number of decimal places presented in the source data with a limitation on maximum of 3 decimal places. Continuous data will be summarized in terms of the mean, standard deviation (SD), median, minimum, maximum and number of observations, unless otherwise stated.

The minimum and maximum will be reported to the same number of decimal places as the raw data recorded in the database. The mean and median will be reported to one more decimal place than the raw data recorded in the database. The SD will be reported to two more decimal places than the raw data recorded in the database. In general, the maximum number of decimal places reported shall be four for any summary statistic.

Departure from these general rules will be specified in the output shell document.

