4.11.3 Clinical Laboratory Evaluation

The following safety laboratory parameters will be measured:

Hematology: Hematocrit, Hemoglobin, Platelet count, Red blood cell count, White blood cell count with differential, Neutrophils, Eosinophils, Basophils, Monocytes, Lymphocytes, Activated partial, thromboplastin time.

Clinical Chemistry: Albumin, Alkaline phosphatase, Alanine aminotransferase, Aspartate aminotransferase, Bilirubin (total and conjugated), C-reactive protein, Calcium, Chloride, Creatinine, Creatine phosphokinase, Gamma-glutamyl transferase, Glucose, Potassium, Sodium, Total cholesterol, Total protein, Triglycerides, Tryptase, WOCBP Only (per SoA): Human chorionic, gonadotropin.

Viral Serology: Hepatitis B surface antigen, Hepatitis B core antigen antibody, Hepatitis C virus antibody, HIV antibody (HIV1 and HIV2), COVID-19, Tuberculosis (quantiFERON Gold™ test).

Urinalysis: Protein, Glucose, Red blood cells, White blood cells, Ketone bodies, pH.

At discretion of Investigator based on urinalysis results:

- Microbiology
- Urine microscopy

Drugs of Abuse: Alcohol, Amphetamines/methamphetamines, Barbiturates, Benzodiazepines, Cannabinoids, Cocaine, Opiates.

Individual data listings of all the laboratory results will be presented for each participant. Flags will be attached to values outside of the laboratory's reference limits along with the investigator's assessment. Clinically significant laboratory test abnormalities that were considered adverse events by the investigator will be presented in the adverse event listings.

Any laboratory parameters with results from the laboratory given as '<xx' or '>xx' in the database will be imputed with the absolute value of the number without the sign (e.g., < 9.2 will be imputed as 9.2) for the descriptive statistics and changes from baseline.

Safety laboratory tests (observed values and change from baseline) will be summarized descriptively in tabular format by dose cohort and pooled placebo group. The baseline for the laboratory parameters will be the measurement obtained prior to administration of IV of XTMAB-16. .

In order to compare a before-and-after effect for selected laboratory parameters, shift tables with regards to reference ranges will be provided for each dose step, and for all participants.

The number and percentage of participants with newly occurring liver enzyme abnormalities occurring at any time post-baseline will be summarized by dose cohort and by overall.

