4.11.4 Vital Signs, Physical Findings and Other Observations Related to Safety

Vital Signs

Oral, tympanic or temporal body temperature, respiratory rate, pulse, and systolic and diastolic blood pressure will be assessed.

Vital signs data will be listed by participant including changes from baseline. The baseline for the vital signs' measurements will be the measurement obtained prior to administration of IV of XTMAB-16.

Table 7 Grading for Vital Signs

Vital Signs *	Mild (Grade 1)	Moderate(Grade 2)	Severe (Grade 3)	Potentially Life Threatening (Grade 4)
Fever (°C) ** (°F) **	38.0 – 38.4 100.4 – 101.1	38.5 – 38.9 101.2 – 102.0	39.0 – 40 102.1 – 104	> 40 > 104
Tachycardia - beats per minute	101 – 115	116 – 130	> 130	ER visit or hospitalization for arrhythmia
Bradycardia - beats per minute***	50 – 54	45 – 49	< 45	ER visit or hospitalization for arrhythmia
Hypertension (systolic) - mm Hg	141 – 150	151 – 155	> 155	ER visit or hospitalization for malignant hypertension
Hypertension (diastolic) - mm Hg	91 – 95	96 – 100	> 100	ER visit or hospitalization for malignant hypertension
Hypotension (systolic) – mm Hg	85 – 89	80 – 84	< 80	ER visit or hospitalization for hypotensive shock
Respiratory Rate – breaths per minute	17 – 20	21 – 25	> 25	Intubation

* Subject should be at rest for all vital sign measurements.

** Oral temperature; no recent hot or cold beverages or smoking.

*** When resting heart rate is between 60 – 100 beats per minute. Use clinical judgement when characterizing bradycardia among some healthy subject populations, for example, conditioned athletes.

Toxicity grading of vital signs will be summarized by dose cohort.

Descriptive statistics (n, mean, SD, median, minimum, maximum) for absolute values and changes from baseline will be presented by dose cohort.

ECG

Standard safety 12-lead ECGs will be performed as shown in the Schedule of Assessments.

The following ECG parameters will be recorded:

P wave, QRS complex, U wave, QRS duration, QT interval, QTcF, T wave, ST segment, RR interval, PR interval, and qualitative results.

The ECG will be evaluated by the Investigator as 'Normal', 'Abnormal, NCS' or 'Abnormal, CS'.

All ECG parameters will be listed by participant for each dose cohort and time point including changes from baseline. The baseline for the ECG measurements will be obtained prior to administration of IV of XTMAB-16.

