Descriptive statistics (n, mean, SD, median, lower quartile, upper quartile, minimum, maximum) for absolute values and changes from baseline will be presented by dose cohort and pooled placebo group. A categorical QTc analysis will also be performed.

A summary of the number and percentage of participants with QTcF intervals exceeding some predefined upper limits (e.g. >450ms, >480ms, >500ms for measured values as well as. >30ms, >60ms for changes from baseline) of ECG parameters will be displayed in a frequency table.

Mean QTcF values (\pm SD) over time per dose and pooled placebo will be presented graphically on Safety set.

If findings on telemetry are identified, a further concentration QT analysis (tie-matched QT and QTc analysis for XTMAB-16 and placebo) **may** be further evaluated. ER analysis consists of the following:

1. A linear mixed effects model with Δ QTcF as the dependent variable, drug plasma concentration as a continuous covariate, treatment (active or placebo) as categorical factor, and a random intercept for each participant. Note: concentration values are set to 0 for placebo participants.
2. The predicted mean $\Delta\Delta$ QTcF (placebo corrected, change from baseline) at the observed geometric mean Cmax (i.e., the product with the slope estimate treatment effect [active – placebo]) will be calculated. Two-sided 90% CIs of the estimate will be calculated using a bias-corrected nonparametric bootstrap with 1,000 resamples and participant as the unit of resampling. Note: Bootstrap is used to provide robust estimate for the 90% CI. Resampling will be done independently for the active and the placebo participants. For each resample, the model will be fitted and the predicted mean $\Delta\Delta$ QTcF will be computed at the geometric mean Cmax determined from the resampled data. The 90% CI will be determined from the distribution of resampled predicted values.
3. Decisions to classify the risk QTprolongation induced by XTMAB-16, the upper bound of the two-sided 90% CI for the $\Delta\Delta$ QTcF effect of XTMAB-16 as estimated by ER model should be <10ms at the observed geometric mean Cmax to exclude a risk QT prolongation induced by XTMAB-16. (reference: ICH E14 Guideline: The Clinical Evaluation of QT/QTc Interval Prolongation and Proarrhythmic Potential for Non-Antiarrhythmic Drugs Questions & Answers (R3))

Physical Examination

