- A complete physical examination will include assessments of general appearance, skin; head/neck; pulmonary, cardiovascular, gastrointestinal, external genitourinary (optional), lymphatic, and musculoskeletal systems; extremities; eyes (inspection and vision control); ears, nose; throat; and neurologic status.
- An abbreviated physical examination will include assessments of general appearance; head, ears, eyes, nose, and throat; cardiovascular; respiratory; and gastrointestinal systems (including the abdomen).
- A targeted physical examination may be conducted at any time at the Investigator's discretion and should be limited to systems of clinical relevance (ie, cardiovascular, respiratory, lymph nodes, liver.)

Abnormal physical examination findings will be listed.

Assessment of liver-related changes will include:

- 3 \times -, 5 \times -, 10 \times -, and 20 \times ULN elevations of AST, ALT, and either ALT or AST
- Any elevations of bilirubin: elevated total bilirubin to $>2 \times$ ULN
- Any elevations of ALP $>1.5 \times$ ULN
- Elevation of AST or ALT ($>3 \times$ ULN) accompanied by elevated bilirubin ($>1.5 \times$ ULN, $>2 \times$ ULN)
- Elevation of AST or ALT in temporal association with nausea, vomiting, anorexia, abdominal pain, or fatigue

- Any liver-related deaths and liver-related treatment discontinuations.

Assessment of liver-related changes will be summarized.

4.11.5 Safety Monitoring (Independent Data Monitoring Committee [IDMC], Data Monitoring Committee [DMC], Data and Safety Monitoring Board [DSMB])

Not Applicable.

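### The scheduled-only and first-value rules are not switched off for the QTcF threshold counts or the vital-sign grades, so an unscheduled extreme can go uncounted; for liver tables the rules conflict or are silent.

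*Protocol*

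**What the plan says.** **General rules.** Protocol 9.4 says of the summary tables: "Only scheduled visits and times relative to dosing will be included in the tabulation". It makes no exception for threshold or grade tables, and its next sentence has categorical data summarised by day, week or time. SAP 4.2, which covers all non-PK assessments, adds a default for unscheduled repeats: "the following rule will be applied, unless specified otherwise". After dosing, "then the first (non-missing) value after dosing will be used in descriptive statistics and in the calculation of change from baseline". Before dosing, the last value is used, and an unscheduled visit can supply the baseline.

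**Tables affected.** SAP 4.11.4 plans "A summary of the number and percentage of participants with QTcF intervals exceeding some predefined upper limits", with limits of 450, 480 and 500 ms and changes of 30 and 60 ms. It also says "Toxicity grading of vital signs will be summarized by dose cohort", using Grades 1 to 4. Neither statement says whether unscheduled readings count or whether the worst value is used.

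**Liver and laboratory.** SAP 4.11.3 says that "newly occurring liver enzyme abnormalities occurring at any time post-baseline will be summarized by dose cohort and by overall". Protocol 9.4.2.1 asks for any bilirubin or ALP elevation above its limits and allows shift tables from baseline to each assessment after treatment. For the 3x, 5x, 10x and 20x ULN multiples, SAP 4.11.4 says only "Assessment of liver-related changes will be summarized".

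**Where unscheduled values come from.** Under Protocol 8.2.5, laboratory tests judged clinically significantly abnormal "should be repeated until the values return to normal or Baseline or are no longer considered clinically significant". Protocol 8.2.4 lets the Investigator order additional ECGs.

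**The concern.** By-visit summaries and threshold counts need different inputs. A mean at Day 29 should use the scheduled Day 29 value, because repeats are taken selectively and would distort it. A count of participants who ever crossed a limit should use every post-dose reading, because an extra ECG or repeat measurement is often taken precisely because something looked abnormal. The plan states the first kind of rule and never states the second.

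Safety comes first among the endpoints, and Protocol 9.1 rules out hypothesis tests, so the descriptive tables carry the safety conclusions. The stopping guidance in Protocol 4.1.2.1 includes a QTcF of 500 ms or more and is not confined to scheduled ECGs. The trial team could therefore act on a reading that the final QTcF table does not count.

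**Working it through.** The documents give no figure to reproduce here. The check is a comparison of texts, followed by a calculation for scale.

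**Step 1: which rule reaches which table.**

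| Table | First-value rule (SAP 4.2) | Scheduled-only rule (Protocol 9.4) | Other wording |
|---|---|---|---|
| QTcF change above 30, 60 ms | Reaches it directly, as a change from baseline | Applies | None |
| QTcF above 450, 480, 500 ms | Not named | Applies by default | None |
| Vital-sign grades | Not named | Applies by default | None |
| Newly occurring liver enzyme abnormalities | Not named | Conflicts | SAP 4.11.3: any time after baseline |
| Bilirubin and ALP elevations | Not named | In tension | Protocol 9.4.2.1: any elevation |
| Laboratory shift tables | Arguably reached, since SAP 4.2 treats shift tables as changes from baseline | In tension | Protocol 9.4.2.1: each assessment after treatment |
| ALT/AST 3x to 20x ULN | Not named | Applies only for want of another rule | No time-point rule |

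**Step 2: does the SAP replace the Protocol sentence?** Protocol 9.4.1 leaves analysis details to the SAP. The SAP does not repeat the scheduled-only sentence, but it does not withdraw it either, and SAP 4.14 declares no change to the planned analysis. The SAP 4.2 default yields to a specific rule, but the QTcF and vital-sign entries contain none.

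**Step 3: asymmetry.** For a QTcF change, an unscheduled pre-dose ECG can set the baseline, while a later repeat after dosing cannot enter the change.

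**Step 4: size of one uncounted participant.** Inputs: 9 active and 3 placebo per cohort, two cohorts (Protocol 4.1, SAP 3.1), so 18 active in all and 3 + 3 = 6 in pooled placebo. One participant is 100/n percentage points. Intervals are exact (Clopper-Pearson) 95%; for 0/n the upper limit is 1 - 0.025^(1/n).

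| Group | n | One participant | 0/n: upper limit | 1/n: interval |
|---|---|---|---|---|
| Dose group | 9 | 11.1 points | 33.6% | 0.3% to 48.2% |
| Pooled placebo | 6 | 16.7 points | 45.9% | 0.4% to 64.1% |
| All active | 18 | 5.6 points | 18.5% | 0.1% to 27.3% |

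**Step 5: how often.** The documents give no rate. If each participant has an assumed probability q that the only crossing is unscheduled, the chance that at least one of 18 active participants is uncounted is 1 - (1 - q)^18:

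- q = 1%: 16.5%
- q = 2%: 30.5%
- q = 5%: 60.3%
- q = 10%: 85.0%

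These values of q are illustrations, not estimates.

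**The case against.** The strongest reply is that this is ambiguity rather than a planned exclusion. The Protocol sentence follows a sorting instruction and can be read as governing by-time displays only. The SAP first-value rule names descriptive statistics and change from baseline, not absolute limits or grades. That is fair, and it is why the absolute QTcF and vital-sign counts are affected only by default. It does not help the change categories, which the first-value rule covers expressly.

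The values are also not lost. SAP 4.11.3 and 4.11.4 list laboratory, vital-sign and ECG data by participant, and Protocol 9.4.2.2 tabulates laboratory abnormalities reported as adverse events. Stopping decisions rest on notification within 24 hours, not on these tables. With 24 participants the listings can be read in full. This limits the harm but does not correct a table that shows zero. The frequent blood pressure and heart rate readings during infusion are planned, so a scheduled-only rule does not clearly remove them.

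Five stronger readings are tempting, and the documents do not support them:

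- *The plan excludes unscheduled liver values.* SAP 4.11.3 and Protocol 9.4.2.1 point the other way. The defect there is unreconciled wording.
- *Extremes are usually seen at unscheduled readings.* Nothing shows this. A laboratory repeat under Protocol 8.2.5 follows a value already judged clinically significant, so the first crossing is often in the table and only a later, higher category is lost.
- *The 14-day gaps between later visits measure the loss.* They describe visit spacing. An episode wholly between visits triggers no repeat by itself, and no tabulation rule can recover a sample that was never taken.
- *The bias always favours the drug.* Omitting readings can only lower a count, but the rules apply equally to placebo. One uncounted placebo participant would make active treatment look relatively worse.
- *ALT above 5x ULN alone meets a stopping criterion.* In Protocol 4.1.2.1 that level must last more than 2 weeks; the other criteria need a higher multiple, or a lower one with bilirubin, INR, symptoms or eosinophilia.

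**Conclusion.** The concern holds in limited form. Followed as written, the plan can leave an unscheduled or repeat extreme out of the QTcF change categories and, by default, out of the absolute QTcF counts and vital-sign grades. For liver and laboratory shift tables the instructions are inconsistent, and the ULN-multiple summary lacks a time-point rule.

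The effect is discrete: a row moves from 0/9 to 1/9 or, in pooled placebo, from 0/6 to 1/6. This assumes that every participant in the group contributes data and that the crossing appears only on a reading the rules leave out. How often that would happen cannot be derived from the documents. The point merits correction before the tables are programmed, but it does not suggest that safety data would go unrecorded or unreported.

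**What to change.** 1. In Protocol 9.4 and SAP 4.2, confine the scheduled-only and first-value rules to by-visit descriptive summaries.
2. In SAP 4.11.3 and 4.11.4, state that the QTcF absolute and change categories, vital-sign grades, liver ULN-multiple tables and any worst-value shift tables use each participant's worst post-dose value from all scheduled, unscheduled and repeat assessments.
3. Reconcile Protocol 9.4 with Protocol 9.4.2.1 and SAP 4.11.3 so that the liver and shift tables follow one stated rule. If the Protocol sentence is not amended, record the departure in SAP 4.14, which currently declares no changes.

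The cost is a few sentences and one worst-value derivation. Study conduct and data collection do not change. Some counts may be slightly less favourable.
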